12.8.2 Sample Size Determination

These power calculations are based primarily on the observed Week 12 results of the Study 2 in Atralin™ (tretinoin) Gel, 0.05% NDA 022070 application. This study was a two-arm trial of Atralin™ versus its vehicle and is felt to be a relevant study in NDA 022070 for powering the current study. The next three power calculations are constructed from the results of Study 2.

A sample size of 400 per treatment arm has at least 96% power to detect a statistically significant difference with a significance level of 0.05. The estimated absolute change from baseline in

treatment means were 6.5 and 3.5 for Atralin™ versus its vehicle, respectively, with a standard deviation of 11.3.

A sample size of 400 per treatment arm has greater than 99% power to detect a statistically significant difference with a significance level of 0.05 using the estimated absolute change from baseline in treatment means of 17.8 and 9.9 for Atralin™ versus its vehicle, respectively, with a standard deviation of 24.7.

The sample size estimates for the dichotomized EGSS require a substantially larger enrollment in order to achieve a power of at least 90%. The success rates observed in the second Atralin™ study was 23% for Atralin™ and 14% for its vehicle which is a difference of 9%. Approximately 90% power is achieved with sample sizes of 400 per treatment group, respectively, using a 1:1 randomization.

It is noted that the same differential in success rates was observed in Study 1 (Atralin™ (tretinoin) Gel, 0.05% NDA 022070 application). The success rates observed in the first Atralin™ study was 13% for Atralin™ and 4% for its vehicle which is also a difference of 9%. Using these estimates, more than 99% percent power is achieved with sample sizes of 400 per treatment group.

The clinical study will be conducted under a common protocol at each investigational site and every effort will be made to promote consistency in study execution at each investigational site as well as uniform evaluation of the EGSS evaluation for subjects at the various study visits. The experience in clinical trial execution gained during the execution of several acne studies conducted under the guidance of the Sponsor raises the expectation that the differential between the success rates of the two arms will be greater than 9%. Thus, the power of the EGSS is expected to be at least 95% for sample sizes of 400 subjects in each arm.

Individually and collectively the considerations lead to a choice of randomizing 400 subjects per treatment group.

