11.4.8 Pregnancy

All female subjects of childbearing potential must use an effective method of birth control during the course of the study, in a manner such that risk of contraceptive failure is minimized. Abstinence is allowed as a birth control method.

Before enrolling a female subject of childbearing potential in this clinical trial, the investigator must review the following information about study participation:

- Informed consent requirements
- Contraceptives in current use

Following review of this information and appropriate subject counseling, the investigator or designee and the subject must sign the informed consent before study enrollment.

During the study, all female subjects of childbearing potential should be instructed to contact the investigator immediately if they suspect they might be pregnant (eg, missed or late menstrual period).

If a subject or investigator suspects that the subject may be pregnant prior to study enrollment, the study drug must be withheld until the results of laboratory pregnancy testing are available. If pregnancy is confirmed, the subject must not receive study drug and must not be enrolled in the study. If pregnancy is suspected while the subject is receiving study treatment, the study drug must immediately be withheld until the result of pregnancy testing is known. If pregnancy is confirmed, the study drug will be permanently discontinued and the subject will be followed until the pregnancy comes to term. A Pregnancy Report form will be submitted to the sponsor, initially and at the end of the pregnancy, which includes the outcome of the pregnancy and any complications occurring during the pregnancy or the delivery.

All confirmed pregnancies must be immediately reported to the medical monitor within 24 hours of the investigator's awareness of the pregnancy. All confirmed pregnancies must be reported via confirmed facsimile/email transmission and must be submitted on a SAE and pregnancy report forms within 24 hours of the investigator's awareness of the pregnancy using the same reporting as procedure for an SAE under Section 11.4.6.

12 Statistics

All statistical processing will be performed using SAS® version 9.3 or later unless otherwise stated. Statistical significance will be based on two-tailed tests of the null hypothesis resulting in p-values of 0.05 or less.

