12.1.5 Statistical Hypothesis Testing and Control of Multiplicity

Statistical hypothesis testing for lesion count analyses will use the statistical model introduced in Section 12.1.3 and employs the methods of Section regarding missing values. The analysis of the dichotomized Evaluator's Global Severity Score will be based on the logistic regression test stratified by analysis center and employs the methods of Section 12.1.7 regarding missing values.

The overall Type I error will be controlled by requiring the co-primary efficacy endpoints of each group to be statistically significant. Specifically, failure of any one of the primary efficacy endpoints will invalidate the statistical significance of the secondary efficacy endpoints.

The following stepwise process will be conducted for testing the secondary efficacy endpoints in order to control for multiplicity. These tests will be performed for only the ITT population. The testing process will terminate whenever a statistical test for a step is not significant. All subsequent tests for the remaining steps will be considered not significant. The order of testing is:

Step Number	Secondary Endpoint
1	Percent change in non-inflammatory lesion count from baseline to Week 12
2	Percent change in inflammatory lesion count from baseline to Week 12

The following stepwise process will be conducted for testing the supportive efficacy endpoints in order to control for multiplicity. These tests will be performed for only the ITT population. In order to control for multiplicity failure of any one of the secondary efficacy endpoints will invalidate the statistical significance of the supportive efficacy endpoints. The testing process will terminate whenever a statistical test for a step is not significant. All subsequent tests for the remaining steps will be considered not significant. The order of testing is:

Step Number	Supportive Endpoint
1	Percent change in non-inflammatory lesion count from baseline to Week 8
2	Percent change in inflammatory lesion count from baseline to Week 8
3	Percent change in non-inflammatory lesion count from baseline to Week 4
4	Percent change in inflammatory lesion count from baseline to Week 4
5	Proportion of subjects who have at least a 2 grade reduction at Week 12 from

	baseline in the Evaluator's Global Severity Score
6	Proportion of subjects who have at least a 2 grade reduction at Week 8 from baseline in the Evaluator's Global Severity Score

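### The EGSS power of at least 95% does not follow from a difference above 9 points: at the 14% vehicle rate it needs about 10 points, and the assumed rates are not given

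*Combined protocol and SAP*

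**What the plan says.** Section 12.8.2 (Sample Size Determination) bases its calculations primarily on Study 2 of an earlier tretinoin gel application: "The next three power calculations are constructed from the results of Study 2". The third of these is the EGSS, with success rates of 23% and 14%: "Approximately 90% power is achieved with sample sizes of 400 per treatment group, respectively, using a 1:1 randomization".

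The section then notes Study 1, with 13% and 4%, which is again a 9-point difference: "Using these estimates, more than 99% percent power is achieved with sample sizes of 400 per treatment group".

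Next it says that the sponsor's experience in running acne studies "raises the expectation that the differential between the success rates of the two arms will be greater than 9" (percent), and it concludes: "Thus, the power of the EGSS is expected to be at least 95% for sample sizes of 400 subjects in each arm". No active rate, vehicle rate or size of difference is given for this last figure. The section closes: "Individually and collectively the considerations lead to a choice of randomizing 400 subjects per treatment group".

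Two other statements matter. The opening of Section 12 (Statistics) sets the significance rule: "Statistical significance will be based on two-tailed tests of the null hypothesis resulting in p-values of 0.05 or less". Section 12.1.5 requires success on all three co-primaries: "The overall Type I error will be controlled by requiring the co-primary efficacy endpoints of each group to be statistically significant".

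**The concern.** The 95% is presented as a consequence of a difference above 9 points. For a comparison of two proportions, power depends on the level of the rates as well as on their difference. The section shows this itself, since one 9-point gap gives two quite different powers. A bare lower bound on the difference therefore cannot yield a lower bound on power.

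At the Study 2 rates the EGSS is the least powered of the three co-primaries, so its power is an upper limit on the chance that the trial succeeds. The 95% is the last EGSS power stated before the section draws its considerations together to justify 400 per arm. A reader could take the risk of missing this endpoint to be 5% or less, when the section's primary inputs give about 9%.

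**Working it through.** **Inputs.** n = 400 per arm, 1:1 (Section 12.8.2). Two-sided α = 0.05 (Section 12), so z = 1.96. Success rates 23% vs 14% (Study 2) and 13% vs 4% (Study 1), both from Section 12.8.2. No dropout inflation is stated and missing values are imputed, so 400 is used throughout.

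**Formula.** Two-proportion normal test with pooled variance under the null. With p̄ = (p₁+p₂)/2:

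- SE₀ = √[2p̄(1−p̄)/n]
- SE₁ = √[(p₁(1−p₁)+p₂(1−p₂))/n]
- power = Φ[(p₁−p₂ − 1.96·SE₀)/SE₁]

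**Step 1: reproduce the figures that have inputs.**

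- EGSS, 23% vs 14%: p̄ = 0.185, SE₀ = 0.02746, SE₁ = 0.02727. (0.09 − 1.96×0.02746)/0.02727 = 1.327, so power is 90.8%. The plan says about 90%.
- EGSS, 13% vs 4%: p̄ = 0.085, SE₀ = 0.01972, SE₁ = 0.01946. (0.09 − 1.96×0.01972)/0.01946 = 2.64, so power is 99.6%. The plan says more than 99%.
- First lesion-count calculation, two-sample t test: difference 6.5 − 3.5 = 3.0, SD 11.3, power 96.3%. The plan says at least 96%.
- Second lesion-count calculation: difference 17.8 − 9.9 = 7.9, SD 24.7, power 99.5%. The plan says greater than 99%.

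All four reproduce.

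**Step 2: hold the vehicle rate at 14% and widen the gap.**

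| Rates | Gap (points) | Power |
|---|---|---|
| 23% vs 14% | 9.0 | 90.8% |
| 23.5% vs 14% | 9.5 | 93.2% |
| 24% vs 14% | 10.0 | 95.1% |

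Solving for 95% gives a gap of 9.96 points. Gaps between 9 and 9.96 points meet the stated premise but miss the stated conclusion. At exactly 23% vs 14%, 95% power would take 481 per arm.

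**Step 3: hold the gap at 9 points and vary the vehicle rate.**

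| Rates | Power |
|---|---|
| 13% vs 4% | 99.6% |
| 18% vs 9% | 96.2% |
| 19% vs 10% | 95.2% |
| 21% vs 12% | 93.1% |
| 23% vs 14% | 90.8% |

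A 9-point gap delivers 95% up to a vehicle rate of about 10%. A 10-point gap delivers it up to about 14% (25% vs 15% gives 94.4%).

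**Step 4: sensitivity to method.** At 23% vs 14%, unpooled variance, arcsine, log odds ratio, continuity-corrected and exact-enumeration versions run from 89.2% to 91.0%. With a continuity correction, 95% at a 14% vehicle rate needs about 10.2 to 10.3 points. A simulated Wald log-odds test without center strata gives 90.9% at 23% vs 14% and 95.3% at 24% vs 14%. No two-sided version brings 23% vs 14% to 95%.

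**Step 5: all three co-primaries together, Study 2 inputs.** Whatever the correlation, joint power is at least 0.9633 + 0.9947 + 0.9077 − 2 = 0.866 and at most the smallest marginal power, 0.908.

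**The case against.** The strongest reply is that nothing has been miscalculated. The 95% has no stated inputs for it to contradict, it is worded as an expectation, and the reader has already been given about 90% and more than 99%. It is also attainable: one whole point more than Study 2 (24% vs 14%) gives 95.1%, and the averages of the two cited studies, (23+13)/2 = 18% vs (14+4)/2 = 9%, give 96.2%. The 14% vehicle rate is tied expressly to the Study 2 calculations, not to the later 95% sentence. Finally, nothing depends on the sentence. The section's own EGSS target is at least 90%, which at 23% vs 14% needs 390 per arm, so 400 stands without it.

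Most of this is right. The figure is reachable and hedged, and the sample size is safe. The planned analysis is also a logistic regression with analysis center after multiple imputation, so the decimals above are approximate. The failed inference remains. The 95% is presented as following from a gap above 9 points, and on the basis that the section calls primary it does not. That it would hold under other rates is no defence when those rates are not stated.

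**Conclusion.** The statement is wrong as written, with low practical impact. A difference above 9 points does not imply at least 95% EGSS power with 400 per arm. At a 14% vehicle rate 95% needs about 10 points, and at a 9-point gap it needs a vehicle rate of about 10% or lower. The shortfall is about 4 percentage points (95% against 90.8%) at the Study 2 rates, and nil at 24% vs 14% or 18% vs 9%. This rests on two-sided 0.05, 400 analyzed per arm and an unstratified two-proportion test. Using 14% as the benchmark follows from the section's own choice of Study 2 as its primary basis.

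**What to change.** Change one sentence in Section 12.8.2, in either of two ways:

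- Delete the 95% sentence and let the figure of about 90 to 91% at the Study 2 rates stand as the EGSS power, keeping the Study 1 figure beside it.
- Make it conditional, for example: If the success rates are 24% vs 14%, power for the EGSS is about 95% with 400 subjects in each arm; at the Study 2 rates (23% vs 14%) it is about 91%. If the sponsor had other rates in mind, stating those resolves the point equally well.

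Optionally, add that all three co-primaries must be significant and that joint power on the Study 2 inputs lies between 86.6% and 90.8%.

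The cost is a less favorable or conditional power statement. Sample size, tests, estimates and enrollment do not change.

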12.8.3 Handling of Missing Data

The method of multiple imputation will be used (see Section 12.1.8).

12.8.4 Multicenter Issues

The study will be conducted at multiple investigational centers in North America and Latin America with the intention of pooling the results for analysis.

12.8.5 Multiplicity Issues

Not applicable.

12.8.6 Windowing Rules

The timing of all study visits is relative to Baseline (Day 0). The Week 4 and Week 8 visits should occur within \pm 3 days of the scheduled times, the Week 12 visit should occur within -3 / +5 days of the scheduled time.

13 Quality Control and Quality Assurance

13.1 Study Monitoring

An Investigator Meeting and/or an initiation visit will be conducted with the principal investigator and study coordinators by sponsor and/or its designee. During this meeting, an extensive review and discussion of the protocol, the role of the study technician, all study procedures, source documents, and eCRFs will be conducted. Evaluation scales will be reviewed extensively and documentation of training will be recorded for training of sponsor-approved evaluators.

The study monitors/clinical research associates will be trained prior to study initiation. Following this training, an overview of the study disease and study material background will be understood. Specific monitoring guidelines and procedures to be followed during monitoring visits will also be utilized. During the course of the study, all data will be 100% source document verified by the monitors. All subject source records must be made available to the monitors.

The conduct of the study will be closely monitored by the sponsor following GCP guidelines. The reports of these verifications will also be archived with the study report. In addition, inspections or on site audits may be carried out by local authorities or by the sponsor's Quality Assurance Department. The investigators will allow the sponsor's representatives and any regulatory agency to examine all study records, corresponding subject medical records, clinical dispensing records and storage area, and any other documents considered source documentation. The investigators agree to assist the representative, if required.

13.2 Audits and Inspections

The study will be conducted under the sponsorship of Valeant in conformation with all appropriate local and federal regulations, as well as ICH guidelines. Interim and end of study audits of raw data, study files, and final report may be conducted by Valeant's Quality Assurance Department or designee.

The sponsor is responsible for implementing and maintaining quality assurance and quality control systems to ensure that studies are conducted and data are generated, documented, and reported in compliance with the protocol, GCP, and applicable regulatory requirements. In addition, the sponsor will be responsible for securing agreement from all involved parties to ensure direct access to all study related investigational centers, source data/documents, CRFs,

and reports for the purpose of monitoring and auditing by the sponsor, and inspection by domestic and foreign regulatory authorities.

13.3 Data Quality Assurance

All assessments performed will be accurately documented in the subject's source documents and CRFs. The investigator or designee will enter the information required by the protocol into the source documents and CRFs provided by the sponsor or designee. Subjects will be identified in the CRFs by their assigned subject number and initials only.

The investigators must read the protocol thoroughly and must follow the instructions exactly. Any deviations should be agreed to by prior discussion between the sponsor and the investigator, with appropriate written protocol amendments made prior to implementing the agreed changes. Any amendment containing major modifications (particularly if it may involve an increased risk to the subjects) will be approved by the IRB before it may be implemented. No change in the conduct of the study can be instituted without written approval from the sponsor.

14 Ethics and Administrative Issues

14.1 Ethical Conduct of the Study

This study will be conducted in accordance with the ethical principles originating from the Declaration of Helsinki, ICH guidelines, GCP, and in compliance with local regulatory requirements. The investigator agrees, when signing the protocol, to adhere to the instructions and procedures described in it and thereby to adhere to the principles of GCP.

14.2 Ethics Review

This protocol, proposed informed consent form and other information to subjects, and all appropriate amendments will be properly reviewed and approved by an Institutional Review Board (IRB) or Independent Ethics Committee (IEC). A signed and dated notification of the IRB/IEC approval will be provided to the sponsor and investigator prior to study initiation. The name and occupation of the chairman and members of the IRB/IEC will be supplied to the sponsor. The investigator will provide required progress reports and report all SAEs to the IRB/IEC as required by the IRB/IEC.

14.3 Written Informed Consent

Written informed consent/assent, in accordance with local clinical investigation regulations, must be obtained prior to participation in the study. The investigator or designee will discuss the purpose of the study with each subject, and provide a description of the study drug (including any potential and possible side effects) and the study procedures. Information must be given both in oral and written form. Subject information will be provided in a language understandable to the subject and may not include any language that appears to waive any of the subject's legal

rights or appears to release the investigator, the sponsor or the institution from liability or negligence.

The investigator will provide the prospective subject sufficient time to consider whether or not to participate, minimizing the possibility of coercion or undue influence and will discuss any questions the subject may have. The investigator will explain to the subject that participation in the study is voluntary and that withdrawal from the study is possible at any time without detriment to care. The consent must include acknowledgment that medical records and medical data derived from the study may be forwarded to the sponsor or to responsible local or federal authorities.

No subject can enter the study or have any study related procedures performed before his/her written informed consent has been obtained. The original signed and dated informed consent form will be retained with the study records, and a copy of the signed form will be given to the subject.

An informed consent template will be supplied by the sponsor. Any changes to the informed consent form must be agreed to by the sponsor or designee prior to submission to the IRB/IEC, and a copy of the approved version must be provided to the sponsor or designee after IRB/IEC approval.

14.4 Subject Data Protection

Subject data will be protected by ensuring that no captured data contain subject names, addresses, telephone numbers, email addresses, or other direct personally identifying information. It is acknowledged that subject initials, demographics (including birthdates), medical histories, and prior concomitant medication uses, along with the name and address of the enrolling investigator may allow for personal identification of study participants. Other than where necessary to meet regulatory requirements, all data collected in this study will be presented in tabulated (ie, aggregate) form and listings containing information that could be used to identify an individual subject will not be included in any public disclosures of the study data or the study results.

14.5 Data Monitoring Committee

Not applicable.

14.6 Financial Disclosure

Financial disclosures will be obtained from all investigators in order to document any potential conflicts of interest.

14.7 Investigator Obligations

The investigator agrees, when signing the protocol, to adhere to the instructions and procedures described in it and thereby to adhere to the principles of Good Clinical Practice (GCP).

14.8 Changes to the Protocol

The investigators must read the protocol thoroughly and must follow the instructions exactly. Whenever possible, any planned deviations should be agreed to by prior discussion between the sponsor and the investigator, with appropriate documentation of sponsor approval prior to effecting the changes agreed upon. Any amendment to the protocol containing major modifications (particularly if it may involve an increased risk to the subjects) will be approved by the IRB before it may be implemented. No change in the conduct of the study can be instituted without written approval from the sponsor.

14.9 Confidentiality/Publication of the Study

All the data furnished to the investigator and his/her staff and all data obtained through this protocol will be regarded as confidential and proprietary in nature and will not be disclosed to any third party, except for the FDA or other regulatory body, without written consent from the sponsor.

15 Data Handling and Record Keeping

